## 10. 8 STUDY ASSESSMENTS AND PROCEDURES

1. 8.1 ENDPOINT AND OTHER NON-SAFETY ASSESSMENTS

**Research Measures for BE WITH**  
**Socialization**

1. University of California, Los Angeles Loneliness Scale (UCLA) measures loneliness

[https://fetzer.org/sites/default/files/images/stories/pdf/selfmeasures/Self\\_Measures\\_for\\_Loneliness\\_and\\_Interpersonal\\_Problems\\_UCLA\\_LONELINESS.pdf](https://fetzer.org/sites/default/files/images/stories/pdf/selfmeasures/Self_Measures_for_Loneliness_and_Interpersonal_Problems_UCLA_LONELINESS.pdf)

2. Social Provisions Scale (SPS-5) measures social needs (table 2).

<https://www.canada.ca/en/public-health/services/reports-publications/health-promotion-chronic-disease-prevention-canada-research-policy-practice/vol-39-no-12-2019/original-quantitative-research-social-provisions-scale.html>

**Health and Wellbeing**

3. Generalized Anxiety Disorder (GAD-7) measures anxiety.

[https://adaa.org/sites/default/files/GAD-7\\_Anxiety-updated\\_0.pdf](https://adaa.org/sites/default/files/GAD-7_Anxiety-updated_0.pdf)

4. Patient Health Questionnaire (PHQ-9) measures depression.

[https://med.stanford.edu/fastlab/research/imapp/msrs/\\_jcr\\_content/main/accordion/accordion\\_content3/download\\_256324296/file.res/PHQ9%20id%20date%2008.03.pdf](https://med.stanford.edu/fastlab/research/imapp/msrs/_jcr_content/main/accordion/accordion_content3/download_256324296/file.res/PHQ9%20id%20date%2008.03.pdf)

5. Short Form Health Survey (SF-12) measures quality of life.

<https://www.hoagorthopedicinstitute.com/documents/content/SF12form.pdf>

6. Interpersonal Needs Questionnaire (INQ-15) measures suicide desire. The team will be using the thwarted belongingness scale only due to results from previous study.

<https://psy.fsu.edu/~joinerlab/measures/INQ-15.pdf>

7. Session rating scale measures the quality of the therapeutic alliance between a counselor and a client. This scale was adapted from a clinical context to assess the alliance between the older adult client and the volunteer/provider.

<https://www.uvm.edu/~cpincus/Session%20Rating%20Scale.pdf>

Measure	Acronym	What it measures	When to measure	Reliability/ Validity	Number of items	Sponsor (ACL) Category

University of California, Los Angeles Loneliness Scale	UCLA	Loneliness	All time points	Cronbach's alpha: 0.72  Discriminant validity and convergent validity demonstrated	3 items	Category 2: Socialization
Generalized Anxiety Disorder	GAD-7	Anxiety	All time points	Cronbach's alpha: 0.92  Good criterion, construct, factorial and procedural validity demonstrated	7 items	Category 3: Health and Well-being
Patient Health Questionnaire	PHQ-9	Depression	All time points	Cronbach's alpha: 0.89  Good concurrent validity when compared with SRQ-20 (71%, $p < 0.001$ ) and construct validity demonstrated	10 items	Category 3: Health and Well-being
Social Provisions Scale	SPS-5	Social Needs Being Met	All time points	Cronbach's alpha: 0.88  Criterion-related and structural validity demonstrated	5 items	Category 2: Socialization
Short Form Health Survey	SF-12	Quality of Life	All time points	Reliability: test-retest correlation of 0.76 for 12-item Mental Component Summary (MCS)	12 items	Category 3: Health and Well-being

				Relative validity estimates for 12-item MCS ranged from 0.60 to 1.07 (median = 0.97) in relation to 36-item short-form scale		
Interpersonal Needs Questionnaire	INQ-15	Suicide Desire-thwarted belongingness scale only	All time points	
Reliability: Thwarted Belongingness - Cronbach's alpha: ~ 0.85
 
Good construct validity (thwarted belongingness correlated significantly with loneliness and low social support) and criterion-related validity (thwarted belongingness uniquely predicts current suicidal ideation: odds ratio = 1.59, <math>p < .01</math>)
	15 items (8 TB)	Category 3: Health and Well-being

*\*\*Please review the table below for a summary of the main mental health measures utilized in this PN-RCT.*

Participant screening includes administration of the UCLA, INQ, and SPS, scoring them, and assigning a risk tier. Participants that are middle or high risk will be enrolled in the trial, whereas those that are low risk do not meet eligibility and will be called back to clarify/answer any questions they may have. Measures will be scored the same day, risk tiers and randomization assigned the same day, whereas the call backs to participants may take up to 72 hours.

Trained graduate student data collectors will be administering all assessments via the phone verbally to older adults. Each received training and administered the measure set, was provided with feedback, and made adjustments to ensure that the measures were administered with fidelity across the trial. Further,

there were notations in Qualtrics to indicate reverse coded items, etc., in which wording may be particularly confusing to older adults to remind data collectors to slow down, repeat, and/or rephrase to ensure that the older adult understood each and every item.

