## 1 PROTOCOL SUMMARY

### 1.1 SYNOPSIS

Title:	ADDRESSING SOCIAL ISOLATION, LONELINESS, AND ELEVATED SUICIDE RISK AMONG VULNERABLE OLDER ADULTS THROUGH AN 8 WEEK CARING CONTACTS TREATMENT: A PARTIALLY NESTED RANDOMIZED CONTROLLED TRIAL
Grant Number:	90INNU0021-03-00
Study Description:	
This PN-RCT evaluates an 8-week caring contacts treatment that is delivered to older adults (urban racially diverse, suburban, and/or rural) in 20-30 minute warm calling "dosages", over 3 conditions. Conditions include 2 treatment (i.e. treatment provided by helpers trained in a standardized and manualized Belongingness and Empathy training grounded in narrative reminiscence and the befriending literature (BE), and treatment provided by helpers trained in BE plus a standardized, manualized, and evidence-based suicide intervention training, the Aging Variant of LivingWorks ASIST (BE WITH), and 1 control (no treatment). Hypotheses include: (a) participants in the BE and BE WITH treatment conditions will experience significantly more improvement across measures than those in the control condition over the course of the 8-week treatment and (b) outcome improvements for those in treatment conditions will be more pronounced for those who begin the period at greater risk.

Objectives * :	
Primary Objective: To develop BE WITH Innovation and equip the Aging Services Network (ASN) with proven skills to reduce social isolation, loneliness, and elevated suicidality and promote social support/well-being with older adults receiving nutrition services.
 
Secondary Objectives: To validate and replicate BE WITH

Endpoints * :	
Primary Endpoint: Reduction in social isolation, loneliness, and elevated suicidality and improved social support/well-being for older adult participants receiving nutrition services.
 
Secondary Endpoints: Improved frequency of empathic and suicide intervention best practice behaviors by trained volunteers

Study Population:	Target $n = 540$ to adequately power the PN-RCT; men and women, aged 65 or older, receiving nutrition services, without instance of dementia or cognitive impairment, and in the state in the Southeastern US.
Description of Sites/Facilities Enrolling Participants:	There will be three Area Agencies on Aging, and 25 senior centers that will be involved in this clinical trial.

**Description of Study  
Intervention/Experimental  

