## 4. 3 OBJECTIVES AND ENDPOINTS

Objective	Metric/Variable	Hypothesis/role/endpoint	Analysis
-----------	-----------------	--------------------------	----------

Validate the BE WITH innovation	Reduce loneliness, and elevated suicidality, and increase the degree to which social needs are met	Over the 8-week treatment loneliness and suicide desire (as measured by the UCLA loneliness scale, Interpersonal Needs Questionnaire) will be significantly decreased, and the variable of social needs being met (as measured by the social provisions scale) will be increased for both treatment groups	Longitudinal growth modeling
Validate the BE WITH innovation	Three treatment conditions	Those older adult participants randomly assigned to the BE or BE WITH treatment condition will demonstrate significant improvements in mental health outcomes when compared with the control group	Longitudinal growth modeling
Validate the BE WITH innovation	Risk tier	Those older adults that start the 8-week treatment at medium or high risk will have statistically significant improvements when compared with those of low risk	Longitudinal growth modeling
Validate the BE WITH innovation	Provider effects	Determine if there is variance in outcomes as a result of the provider assigned. 60 providers were trained in either BE or BE WITH and carried caseloads of older adult clients enabling the nesting of effects to determine if there are individual or group level provider effects	Multilevel modeling
Validate the BE WITH innovation	Improved quality, frequency of empathic and suicide intervention best practice behaviors by trained NS providers	An augmented version of Gould's (2013) coding protocol was developed to quantitatively behaviorally code treatment call dosages.	independent quantitative behavioral coding, double coding, 2 protocols, inter-rater agreement, coefficient kappas

The main overarching objective of the clinical trial is to validate the 8-week BE WITH warm calling program, equipping the Aging Services Network (ASN) with proven skills to reduce social isolation, loneliness, and elevated suicidality, while also promoting social support/well-being. The goal of the validation objective is to garner the evidence needed to get the first such program on the National Council on Aging's Evidence Based Registry.

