
Reduction in loneliness, elevated suicidality, and improved social support/well-being for older adult clients
 
Validated constructs (see appendix D):
 
Loneliness (UCLA); Social Support (SPS); Suicide -- Risk (SBQ-R); Suicide Desire (INQ); Suicide Capability (FAD); Depression (PHQ); Anxiety (GAD); Distress (K6);
	
540 Clients, randomly assigned to 3 conditions. This includes the 2 tx conditions and a control that receive no calls
 
Stratified random sampling by 3 levels of loneliness and suicidality (low, medium, and high risk tiers)
	
Data collection for older adult participants:
 
 
· pre intervention (baseline)
 
· measurement occasions every 2 weeks (total of 5 measurement occasions)
 

Improved frequency of empathic and suicide intervention best practice behaviors by NS volunteers
 
Coded constructs: Adapted observation protocol.
	
60 Volunteers, randomly assigned to 2 conditions.
 
 
· BE training only
 
· BE WITH (BE training plus ASIST)
 
 
Those trained in BE will be offered ASIST after the study.
	
Preceding the intervention study, all volunteers receive BE (phone-based social connection) training. BE WITH volunteers will be given the standardized and manualized ASIST training (if they have previously received ASIST, they will be provided with the ASIST refresher training).

---	---	---

**Validated outcome measures** are essential for effective evaluation of any mental health or suicide prevention programming. While the social isolation, loneliness, and elevated suicidality constructs we will study are listed in the following table, the specific psychological scales that measure them are listed and explained in Appendix D. The comprehensive battery of assessments has been field tested and well received by older adults (Appendix D). We have also completed cognitive interviews (administered questions and sought feedback on the experience from older adults), and trained data collectors to use a conversational style in speaking with participants. Short forms of several of these measures will be completed weekly by the older adults and take 15 minutes to complete.

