## 6. 5 STUDY POPULATION

### 1. 5.1 INCLUSION CRITERIA

In order to be eligible to be a **participant** in this study, an individual must meet all of the following criteria:

1. Provision of verbal informed consent
2. Classify as an Older Adult (65+)
3. Stated willingness and ability to comply with all study procedures
4. Receive nutrition services through the Aging Services Network (i.e. either HDM (home delivered meals services) or CM (congregate meals))
5. Be affiliated with one of the 25 senior centers we will contract with through a Memorandum of Understanding

In order to be eligible to be a **trained helper** in this study, an individual must meet all of the following criteria:

1. Provision of written informed consent
2. State willingness to comply with all study procedures
3. Be a staff or volunteer within the ASN (Aging Services Network), specifically within the 25 senior centers we are working with
4. Meet criteria for being a “natural helpers” (i.e. be warm, empathic, and having ongoing interaction with participants through one’s job role)
5. Be recommended by the senior center leadership as meeting these qualifications

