### 2. 5.2 EXCLUSION CRITERIA

**Exclusion criteria for Participants:** An individual who meets any of the following criteria will be excluded from participation in this study:

1. Had a dementia diagnosis, or another form of cognitive impairment, and/or hearing impairment that would preclude phone conversation.
2. Participation in another warm calling behavioral treatment or intervention study simultaneously occurring in this state

The reasons given to exclude participants with dementia/cognitive impairment diagnoses from large-scale clinical research are partially related to the concern of a potential risk of abuse and exploitation. Further, those with cognitive impairment are not able to give informed consent, and there are measurement challenges with behavioral health data.

**Exclusion criteria for trained natural helpers:** An individual who meets any of the following criteria will be excluded from participation in this study:

1. Does not have ongoing interactions with potential old adult participants (i.e. is a part of an optimized nutrition service provider in which they do not serve the same older adults consistently over time)
2. Participation in another warm calling behavioral treatment or intervention study simultaneously occurring in this state

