### 3. 9.3 POPULATIONS FOR ANALYSES

The population for analysis includes all randomized participants who met inclusion criteria. We are using the Intention-to-Treat (ITT) Approach, meaning that even those participants that had an AE or dropped out of the treatment will still be included.

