Since the clinical trial is structured to occur in cohorts, the longitudinal multilevel modeling (growth modeling) analysis will be run after each cohort is completed. Despite early cohorts being underpowered, we find significant value in understanding if the data are trending in the expected directions, and/or if there are any issues that need to be addressed. The methodologist running the analysis will remain unblinded throughout the analysis process. There are no temporary suspension or safety findings that would prompt temporary suspension of the treatment. The frequency of monitoring the end points is daily as older adult participants are on a rolling recruitment and finishing their treatment at different points in time. There is no effect of the interim analysis on the final analysis as it is the same analysis. Type I error results when running many different types of tests, however we are running the main analysis with an underpowered sample so that we are learning and understanding as we go. The final analysis will be the same code just with all the participants across all 4 cohorts.

---

7. 9.4.7 SUB-GROUP ANALYSES

Sub-group analyses on the primary endpoints will be assessed in two ways: (a) multi-level modeling by treatment severity group (same primary analysis, conducted independently for low, medium, and high risk patients), and (b) cluster analysis to explore any potential differential treatment effects across predefined patient subgroups (e.g., age, sex, race, etc.). Interaction terms between any subgroup variables (i.e. age, sex, baseline severity) and treatment condition will be included to assess whether the trajectory of outcomes over time varied by subgroup. This approach will enable the examination of both between- and within-patient variability while accounting for repeated measures and clustering.

Since the secondary endpoints are serving as a fidelity check (i.e. trained helpers increased skills, retained skills, etc.) and were are only planning for approximately 60 trained helpers, which would be under powered, any differences in sub-groups, we imagine will be challenging to detect. Despite this,

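### Section 8.1 bars low-risk people from the trial, while Sections 3 and 9.4.7 plan analyses that need them

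*Combined protocol and SAP*

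**What the plan says.** Section 8.1 describes screening with the UCLA, INQ and SPS, scoring, and assignment of a risk tier. It then says: "Participants that are middle or high risk will be enrolled in the trial, whereas those that are low risk do not meet eligibility".

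Two passages plan an analysis of low-risk participants:
- Section 3, risk-tier row: people who start the treatment "at medium or high risk will have statistically significant improvements when compared with those of low risk".
- Section 9.4.7, subgroup approach (a): "same primary analysis, conducted independently for low, medium, and high risk patients".

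Two more name a low tier in the sample to be randomised:
- Section 4.1, for the 540 clients: "Stratified random sampling by 3 levels of loneliness and suicidality (low, medium, and high risk tiers".
- Section 6.3 scores baseline data into low, medium or high and then randomises. It mentions no exclusion between the two steps.

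The places where a reader looks for eligibility do not carry the rule. The Synopsis population is "men and women, aged 65 or older, receiving nutrition services, without instance of dementia or cognitive impairment". Section 5.1 lists five inclusion criteria for participants under the words "an individual must meet all of the following criteria", and Section 5.2 lists two exclusion criteria; none concerns tier or score. Section 5.4 ties ineligible screen failures to the exclusion criteria, which do not include low risk.

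Section 9.3 sets the analysis population: "The population for analysis includes all randomized participants who met inclusion criteria".

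**The concern.** Eligibility decides who is enrolled and to whom the result applies. Here one section removes a group that the objectives table and the subgroup plan both use. Staff following 8.1 would turn low-risk callers away; staff following 6.3 with the lists in 5.1 and 5.2 would randomise them. A reader of the results could not tell whether the effect describes at-risk older adults or nutrition-service clients in general, and the stated goal is evidence for a national registry.

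Timing matters as well. Section 9.4.6 runs the growth model after every cohort. If low-risk people have been randomised and their handling is settled only after cohort results have been seen, that decision could depend on the data.

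**Working it through.** The check is mainly a comparison of passages, with a little arithmetic. Middle (8.1) and medium (elsewhere) are taken to be the same tier.

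**1. Is there one tier variable or two?** The schedule in Section 1.3 puts the baseline survey, its scoring and random assignment all in Week 1. Section 6.3 derives the tier from baseline data, then randomises people one by one. Section 8.1 puts scoring, tiering and randomisation on the same day. The documents therefore describe a single tier, fixed before randomisation. Section 3 also speaks of the tier at the start of treatment. A separate screening tier and analysis tier would remove the conflict, but none is described.

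**2. Follow 8.1.** Low tier: n = 0.
- Section 3 contrast, medium or high against low: the reference group has 0 people, so the contrast cannot be estimated.
- Section 9.4.7: 3 tier models planned, 3 − 1 = 2 with data.
- Synopsis hypothesis (b), more improvement under treatment for those who start at greater risk: still testable as high versus medium.

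**3. Follow Sections 3 and 9.4.7.** Low-risk people are randomised. The filter in 9.3 is the inclusion criteria. Section 5.1 is the only participant list with that heading, and none of its five items concerns tier. Low tier is therefore no ground for removal, and the intention-to-treat sentence in 9.3 points the same way. These people stay in the analysis while 8.1 calls them ineligible. The documents give no low-tier share, so their number cannot be derived.

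**4. Does the conflict reach the sample size?** Inputs from Section 9.2: effect 0.40, Type I error 0.05 (two-sided assumed), power 0.80, ICC 0.20, R² 0.50, 6 clients per volunteer. The 270 is read as 15 volunteers and 90 clients in each treated arm plus 90 controls, with clustering in the treated arm only.
- Variance = (1 − R²) × [(1 + (m − 1) × ICC)/n_t + 1/n_c] = 0.50 × [(1 + 5 × 0.20)/90 + 1/90] = 0.50 × 3/90 = 0.0167.
- SE = 0.129; 0.40/0.129 = 3.10. A noncentral t with 15 − 1 = 14 degrees of freedom gives power 0.821.
- 15 is the smallest number of volunteers per treated arm that reaches 0.80: 15 × 6 × 3 = 270, the plan's figure.
- The target of 540 is 3 × 180, and 30 volunteers × 6 = 180 per treated arm.

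No term involves tier, so neither figure changes.

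**5. Do the recruitment numbers show which rule is meant?** Section 5.5 screens 3 × 540 = 1,620 and enrols at least 540 + 200 = 740. That leaves 1,620 − 740 = 880 people, and 880/1,620 = 54.3%. The 8.1 rule fits this plan only if the low tier and all other losses together are at most about 54% of those screened. Without a stated low-tier share, the numbers do not settle it.

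**The case against.** The strongest case for the plan is that much of this is omission. Criteria that must all be met are necessary conditions, and Section 5.1 does not say that they are sufficient. An extra rule in 8.1 leaves the Synopsis, 5.1 and 5.2 incomplete without contradicting them. Section 4.1 only names a three-level factor, and a level that screening leaves empty breaks nothing. Some text also fits 8.1: the script in 5.5 says a survey decides eligibility, 6.4 mails the participation plan after eligibility is met, and the opening definition in 5.4 covers anyone who consents and is not randomised. All of this stands. It narrows the direct contradiction to 8.1 against Sections 3 and 9.4.7, with 4.1 and 6.3 in tension and the criteria lists incomplete. It does not remove the contradiction, because none of the compatible passages states that low tier is the rule.

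A reader might infer more than the documents support:
- That the trial loses power or its primary comparison fails. Neither Section 9.2 nor the primary analysis in 9.4.2 uses tier.
- That the analysis set is undefined. Taken literally, 9.3 and 5.1 keep randomised low-risk people; the difficulty is that 8.1 calls the same people ineligible.
- That the risk hypothesis is lost altogether. Synopsis hypothesis (b) survives as high versus medium.

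**Conclusion.** The inconsistency is real and must be fixed. Under 8.1, one row of the Section 3 objectives table has no comparator and 1 of the 3 tier models in 9.4.7 has no data. Under the alternative, people whom 8.1 declares ineligible are randomised and analysed, in a number the documents do not allow one to derive. The case for fixing it rests chiefly on the unsettled trial population, since the certain analytic loss is limited to those two items.

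The conclusion assumes one tiering step before randomisation, as Sections 1.3, 6.3 and 8.1 describe. It does not depend on the tier cut-offs, which the available text does not show, and it takes no position on which population is the right one.

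**What to change.** Reconcile the passages in one amendment, with the sponsor choosing the population.

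- **Option A, low risk excluded.** Add the tier criterion to the Synopsis and 5.1/5.2, and name low tier as a screen failure in 5.4. Drop low from the randomisation strata in 4.1 and 6.3 and from the models in 9.4.7; scoring all three tiers at screening can stay. Restate the Section 3 contrast as high versus medium.
- **Option B, low risk included.** Delete the exclusion in 8.1 and align the recruitment script in 5.5.

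Under either option, state in 9.3, before the next cohort analysis, how anyone randomised while low risk is handled, and report their number by arm. Parts of the text are in the past tense, so enrolment may have begun. An amendment cannot change who is already in, which makes that count necessary.

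Cost: one amendment, which the Statement of Compliance requires the IRB to approve before it takes effect, and no new data, because the tier is already scored at baseline. Option A leaves no evidence on low-risk people and gives up only analyses that 8.1 already empties. Option B widens the population beyond 8.1.
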